Additionally, six randomized controlled trials (RCTs) examined the safety or immunogenicity of administering mRNA COVID-19 doses alongside influenza vaccines [14–19]. All these studies have confirmed the safety of administering the vaccines together; however, the findings on immunogenicity were mixed. Out of the six RCTs, five evaluated HIR and observed reduced anti-SARS-CoV-2 antibody concentrations in those receiving both vaccines [15–19]. Only two studies met the non-inferiority margin for immunogenicity outcomes [15, 18]. However, none have yet evaluated CMIR.

Owing to the lack of prior research evaluating CMIR, we conducted a pilot study to assess both HIR and CMIR for COVID-19 and influenza vaccines administered together compared with individually administering each vaccine. We hypothesized that the CMIR may be stronger in the co-administration group, which could help explain the reduced mortality from COVID-19 infections reported in previous studies for patients vaccinated with the influenza vaccine. If confirmed, a stronger CMIR may serve as a proof-of-concept, demonstrating the potential immunological benefits of vaccine co-administration. Additionally, our study may provide insightful findings on the co-administration policy, the implementation of which may increase vaccine coverage and reduce healthcare burden.

Objectives

Primary Objective:

- To evaluate and compare post-vaccination cell-mediated immune responses (CMIR) and humoral immune responses (HIR) between participants receiving co-administration of COVID-19 and influenza vaccines versus COVID-19 vaccine alone.

Secondary Objectives:

- To assess the magnitude of immune responses within each study group.
- To compare the magnitude of immune enhancement between groups.
- To evaluate the frequency and severity of adverse events following vaccination.

Study Design and Participants

This was a pilot, single-blind, randomized controlled trial conducted at Songklanagarind Hospital, Faculty of Medicine, Prince of Songkla University, Hat Yai, Thailand. Eligible participants were healthy adult volunteers aged 18–60 years.

Inclusion Criteria

- Thai adults aged 18–60 years who had received COVID-19 and influenza vaccines more than 6 months prior.
- Able and willing to comply with trial requirements, including 1-month follow-up.
- In good health at enrollment as judged by medical history, physical exam, and investigator assessment.
- Able to provide informed consent and sign the ICF.

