Exclusion Criteria

- History of influenza or COVID-19 infection within 6 months.
- History or family history of convulsions, epilepsy, encephalopathy, or psychosis.
- Allergy to vaccine components or prior severe hypersensitivity reactions.
- History of Guillain-Barré syndrome.
- Positive pregnancy test, pregnant, breastfeeding, or pregnancy plan within 6 months.
- Infectious diseases including HIV or suspected SARS-CoV-2 infection.
- Prior SARS-CoV-2 infection within 6 months.
- Severe uncontrolled chronic diseases (e.g., poorly controlled diabetes mellitus, uncontrolled hypertension).
- History of urticaria within 1 year before vaccination.
- Known coagulation disorders or thrombocytopenia contraindicating intramuscular injection.
- Needle phobia.
- Use of immunosuppressive therapy, cytotoxic therapy, or systemic corticosteroids.
- Receipt of blood products within 4 months before vaccination.

- Ongoing anti-tuberculosis treatment.
- Inability to follow protocol or understand informed consent, as judged by investigator.

Interventions

Arm 1 – Active Comparator: Bivalent mRNA COVID-19 vaccine (BNT162b2)

- Intervention: Biological/Vaccine – Bivalent mRNA SARS-CoV-2 vaccine
- Description: Administering a booster dose of the bivalent mRNA vaccine BNT162b2 (Pfizer, Bangkok, Thailand).

Arm 2 – Experimental: Quadrivalent Influenza Vaccine

- Intervention: Biological/Vaccine – Quadrivalent influenza vaccine
- Description: Administering a VaxigripTetra™ (Sanofi-Aventis, Bangkok, Thailand).

Arm 3 – Experimental: Co-administration

- Interventions:
 - Biological/Vaccine – Bivalent mRNA SARS-CoV-2 vaccine (BNT162b2)
 - Biological/Vaccine – Quadrivalent influenza vaccine (VaxigripTetra™)
- Description: Co-administering both vaccines intramuscularly, either in different arms or in the same arm at least 25.4 mm apart.

Outcomes

Primary Outcomes

- **Cell-mediated immune response (CMIR):** Post-vaccination interferon-gamma enzyme-linked immunospot (IFN- γ ELISpot) assay results comparing the co-administration group with the COVID-19 vaccine-only group.
- **Humoral immune response (HIR):** Post-vaccination anti-receptor-binding domain immunoglobulin G (anti-RBD IgG) concentrations comparing the co-administration group with the COVID-19 vaccine-only group.
- **Non-inferiority margin:** Defined as the lower bound of the 95% confidence interval for the geometric mean ratio (GMR) >0.67 , consistent with WHO vaccine evaluation guidelines.

Secondary Outcomes

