- **Magnitude of immune response within each group:** GMR comparing pre- and post-vaccination values (GMRpost/pre) for both CMIR and HIR.
- **Comparison of immune enhancement between groups:** Ratio of GMRpost/pre values across groups.
- **Adverse events (AEs):** Incidence, type, and severity of local and systemic solicited AEs at 1 and 4 weeks, as well as unsolicited and serious AEs.

Study Procedures

Eligible volunteers provided written informed consent before participation. Participants were randomized in a 1:1:1 ratio, using block randomization (block size of 6) generated with R Statistical Software, to receive:

1. Bivalent mRNA COVID-19 vaccine (BNT162b2, Pfizer) alone,
2. Quadrivalent influenza vaccine (VaxigripTetra™, Sanofi-Aventis) alone, or
3. Both vaccines administered concurrently.

Vaccines were administered intramuscularly, either in different arms or in the same arm with injection sites at least 25.4 mm apart.

Blood samples were collected at baseline (Day 0, prior to vaccination) and at Day 28. Samples were used for measurement of:

- Humoral immune response (HIR): anti-receptor binding domain (RBD) IgG levels.
- Cell-mediated immune response (CMIR): IFN- γ enzyme-linked immunospot (ELISpot) assay.

Participants were monitored for immediate adverse reactions for 30 minutes after vaccination. Active follow-up was conducted at 1- and 4-weeks post-vaccination to assess solicited local and systemic adverse events, and unsolicited or serious adverse events were documented throughout the study period.

Sample Size

A total of 36 participants was planned. The sample size followed Julious' rule-of-thumb[20] for pilot studies (≥ 12 per group) to obtain stable variance estimates and inform the design of a subsequent adequately powered non-inferiority RCT. The study was not powered for confirmatory hypothesis testing; non-inferiority analyses are exploratory. Estimates from this pilot (means, variances, GMRs) will guide the definitive trial's sample-size calculation.

Statistical Methods

Analysis Population

- All randomized participants who received at least one dose of study vaccine were included in the immunogenicity and safety analyses (modified intention-to-treat).

Data Handling and Transformation

- Immune response outcomes (IFN- γ ELISpot and anti-RBD IgG antibody levels) were log-transformed prior to analysis to normalize distributions and stabilize variance.
- Zero values were replaced with 1 to allow logarithmic transformation.

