Primary Analysis

- Geometric mean ratios (GMRs) of post-vaccination responses were calculated to compare the co-administration group with the COVID-19 vaccine-only group.
- Non-inferiority was concluded if the lower bound of the two-sided 95% confidence interval (CI) exceeded **0.67**, consistent with WHO vaccine evaluation guidelines.

Secondary Analyses

1. **Magnitude of immune response (within-group):**
 - Calculated as GMRpost/pre for both CMIR and HIR.
 - Paired t-tests were used to assess the significance of pre- vs post-vaccination changes.
2. **Between-group comparisons (ratio of magnitude):**
 - Ratios of GMRpost/pre between study groups were calculated to compare immune enhancement.
3. **Safety analysis:**
 - Incidences of solicited local and systemic adverse events were summarized by frequency and percentage.
 - Group comparisons used Chi-square or Fisher's exact tests, as appropriate.

Software

- All statistical analyses were conducted using **R Statistical Software, version 4.3.2** (R Foundation for Statistical Computing, Vienna, Austria).

Laboratory Methods

- **Antibody analysis:** Anti-SARS-CoV-2 RBD IgG (Wuhan-Hu-1 strain) will be measured by chemiluminescent microparticle immunoassay (Abbott, Abbott Park, IL, USA). Results in arbitrary units (AU/mL) will be converted to WHO binding antibody units (BAU/mL) using $1 \text{ BAU/mL} = 0.142 \text{ AU/mL}$.
- **Ex vivo IFN- γ ELISpot assays:** Peripheral blood mononuclear cells (PBMCs) will be stimulated with SARS-CoV-2 spike peptide pools (Wuhan strain) and assessed in triplicate wells. Spot-forming cells (SFCs) per 10^6 PBMCs will be quantified using an automated ELISpot counter (AID Diagnostika, Konstanz, Germany), subtracting background from negative controls.

Adverse Event Monitoring

All participants were observed on-site for 30 minutes post-vaccination to detect any immediate reactions.

Solicited Adverse Events (AEs):

- Local AEs: pain, redness, swelling, and palpable mass at the injection site.
- Systemic AEs: fever, myalgia, malaise, headache, nausea, and other constitutional symptoms.

- These pre-specified solicited AEs were actively assessed at 1 week and 4 weeks after vaccination.

Unsolicited and Serious Adverse Events (SAEs):

- Any unsolicited AE reported during the study period was documented.
- SAEs were recorded throughout the follow-up period, with severity grading and assessment of relationship to study vaccines.

Ethics and Dissemination

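### Free improvement: the primary GMR leaves out the Day 0 values already collected; adjusting for log(Day 0) narrows the CI on average once the Day 0–Day 28 correlation exceeds about 0.23, though perhaps little for ELISpot

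*Combined protocol and SAP*

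**What the plan says.** The Primary Analysis section defines the comparison on Day 28 values only: "Geometric mean ratios (GMRs) of post-vaccination responses were calculated to compare the co-administration group with the COVID-19 vaccine-only group". Non-inferiority is judged by whether the lower limit of a two-sided 95% CI exceeds 0.67. The Primary Outcomes section words the antibody endpoint the same way, as post-vaccination "concentrations comparing the co-administration group with the COVID-19 vaccine-only group". Neither section names a model or a covariate.

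Day 0 values exist for both assays. Under Study Procedures, "Blood samples were collected at baseline (Day 0, prior to vaccination) and at Day 28", and those samples serve both anti-RBD IgG and ELISpot. In the analysis plan Day 0 enters only the secondary analyses: the within-group post/pre GMR and its between-group ratio. No margin is stated for either.

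Three other statements bear on the point:

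- Eligibility requires adults "who had received COVID-19 and influenza vaccines more than 6 months prior". There is no upper limit on that interval.
- The Sample Size section says: "The study was not powered for confirmatory hypothesis testing; non-inferiority analyses are exploratory". It also says "Estimates from this pilot (means, variances, GMRs) will guide the definitive" trial's sample size.
- For ELISpot, counts are obtained after "subtracting background from negative controls", and under Data Handling and Transformation, "Zero values were replaced with 1 to allow logarithmic transformation".

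**The concern.** With 12 people per arm the CI for the GMR will be wide, and a measurement that may explain part of the Day 28 variation is left out of the primary comparison. Because the time since the last vaccination is open-ended, Day 0 values may differ a good deal between people. If they predict Day 28, adjustment removes that part of the residual variance. It also corrects for whatever baseline difference chance produces between two small arms.

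The second stake is the definitive trial. The pilot outputs listed for sizing it are means, variances and GMRs. The Day 0–Day 28 correlation and the residual SD after adjustment, which determine whether a baseline-adjusted trial could be smaller, are not listed.

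**Working it through.** **Inputs from the documents.** 36 participants, 1:1:1, at least 12 per group: 3 × 12 = 36, so the planned total reproduces. The primary comparison uses 24 people. The analysis is on the log scale, with a two-sided 95% CI and margin 0.67.

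**Assumed, because the documents are silent.** Correlation r between log Day 0 and log Day 28, varied from 0 to 0.7; normal logs; equal SDs at the two visits; 12 evaluable per arm. Relative widths do not depend on the SD. Where an SD is needed, 0.8 (natural log) is used for illustration.

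**Break-even correlation.** The unadjusted half-width is t(22) × s × √(2/12), with t(22) = 2.0739. Adding log(Day 0) does three things: it multiplies the residual variance by (1 − r²), it reduces the degrees of freedom to 21 (t = 2.0796), and it adds an expected variance factor for chance baseline imbalance of 1 + 1/(22 − 2) = 1.05. Mean squared widths are equal when

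r = √(1 − 2.0739² / (2.0796² × 1.05)) = 0.230.

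On mean width the break-even is 0.225. The lost degree of freedom alone would put it near 0.07, so most of the cost comes from chance imbalance. With 11, 10 or 9 evaluable per arm the squared-width break-even rises to 0.243, 0.258 and 0.277.

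**Width.** The mean width ratio is 1.026 × √(1 − r²). Simulation (at least 100,000 trials per setting) agrees:

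| r | Adjusted / unadjusted CI width | Trials with a narrower CI |
|---|---|---|
| 0 | 1.026 | 20% |
| 0.225 | 1.000 | 40% |
| 0.3 | 0.979 | 53% |
| 0.5 | 0.889 | 85% |
| 0.7 | 0.733 | 99% |

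**The planned post/pre ratio is not a substitute.** With equal SDs its CI width relative to the Day 28-only CI is √(2(1 − r)): 1.18 at 0.3, 1.00 at 0.5 and 0.77 at 0.7. In each case the adjusted analysis is narrower (0.98, 0.89, 0.73).

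**ELISpot zeros.** As an illustration, 1 to 3 of the 24 Day 0 values were set to 1, with an assumed geometric mean of 50 and SD 0.8. Width ratios:

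| r | Zeros are the lowest true values | Zeros fall at random |
|---|---|---|
| 0.3 | 0.99 | 1.00–1.02 |
| 0.5 | 0.91–0.92 | 0.96–1.00 |
| 0.7 | 0.79–0.81 | 0.90–0.97 |

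If the zeros are mostly assay noise, much of the gain goes. Coverage stays at 95% in this model.

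**Passing the margin** (SD 0.8, true GMR 1). The lower limit exceeds 0.67 in 22% of trials unadjusted, and in 22%, 26% and 36% adjusted at r = 0.3, 0.5 and 0.7. If either GMR were allowed to pass, the false non-inferiority rate at a true GMR of 0.67 would rise from 2.5% to 3.3%, 3.7% and 4.1%. One GMR must therefore be declared.

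**Chance imbalance.** The arms differ at baseline by more than 0.5 SD in about 22% of trials. In those, unadjusted coverage is 93%, 90% and 85% at r = 0.3, 0.5 and 0.7, against 95% adjusted. Overall unadjusted coverage is still 95%. In the remaining 78% it is therefore above nominal: at r = 0.7, (0.95 − 0.22 × 0.85)/0.78 ≈ 98%.

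**Definitive trial.** Size per arm = 2 × SD² × (1 − r²) × (1.960 + 1.282)² / (ln 0.67)², for one-sided 2.5% and 90% power. At SD 0.8 and r = 0 this is 2 × 0.64 × 10.51 / 0.1604 = 83.9, so 84. At r = 0.3, 0.5 and 0.7 it is 77, 63 and 43.

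**The case against.** The strongest reply is that nothing is broken. The planned GMR is valid, the protocol calls non-inferiority exploratory, and covariate adjustment is optional in an unpowered pilot. That stands, and it is why this is offered as an improvement and not as a fault.

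The benefit also rests on a correlation the documents do not give. At 0.3 the chance of passing 0.67 is 22% either way. The break-even of 0.23 is an average: at that value only about 40% of trials get a narrower interval, and a single trial is more likely than not to gain only above about 0.28 (interpolating between 44% at 0.25 and 53% at 0.3). All of this stands. It limits the claim without reversing it, because the average loss is at most about 3% and the gain at 0.5 or more is several times that.

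Day 0 is not wholly unused, and the correlation could be recovered if log variances at both visits (v0, v28) and of the change (vd) were reported: r = (v0 + v28 − vd) / (2√(v0·v28)). That is true, but the plan does not commit to reporting all three. A pilot estimate is also imprecise. An observed 0.5 from 24 people has a 95% CI of 0.11 to 0.76 (Fisher z, SE 1/√20), which at SD 0.8 means 83 down to 36 per arm. The SD matters as well: unadjusted, SD 0.5 needs 33 per arm and SD 1.0 needs 132. The correlation informs sizing but does not settle it, so its CI should be reported.

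Finally, results may already be known. Much of the text is in the past tense, while Laboratory Methods uses the future, and one reference was accessed in July 2024, after the document date of 2 January 2024. If so, the primary analysis should not change, and only a labelled addition is open.

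**Conclusion.** The point holds as a free improvement, not an error. The primary GMR is defined on Day 28 values with no covariate, while Day 0 values of both assays are in hand. Adjusting for log(Day 0) keeps the same target GMR on the log scale. On average it costs about 3% in CI width if the correlation is zero and narrows the interval by 11% at 0.5 and 27% at 0.7. These figures assume 12 evaluable per arm, normal logs and a linear relation. The true correlation is unknown for both assays, and for ELISpot the gain may be small. Adjustment does not make 12 per arm adequately powered: even at a correlation of 0.7 the chance of passing 0.67 is only 36% under the assumed SD of 0.8. Reporting the correlation and residual SD is useful to the pilot's stated purpose even if adjustment gains nothing in this sample.

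**What to change.** First state in the SAP whether any Day 28 result has been seen.

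- **If none has been seen:** for each assay, declare as primary the exponentiated arm coefficient, with 95% CI, from a linear model of log(Day 28) on arm (co-administration versus COVID-19 vaccine only) and log(Day 0). Judge only that GMR against 0.67, and keep the unadjusted GMR as a sensitivity analysis.
- **If results have been seen:** keep the planned unadjusted GMR as primary and judge only that one against 0.67. Report the baseline-adjusted GMR with its 95% CI beside it, labelled as added later.

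In both cases leave the secondary ratio of post/pre GMRs as it is. For each assay report the residual SD, the Day 0–Day 28 log correlation with its CI, and the number of Day 0 zeros per arm.

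The cost is two sentences of SAP text and one linear model per assay, with no new samples or visits. A participant without a Day 0 result would drop out of the adjusted model only.

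### The safety comparison names no pair of arms and plans no between-group effect estimate or interval, so its tests say little about what co-administration adds

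*Combined protocol and SAP*

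**What the plan says.** Three arms are compared: "Participants were randomized in a 1:1:1 ratio" (Study Procedures). The Sample Size section states "A total of 36 participants was planned", on a rule of thumb "for pilot studies (≥ 12 per group) to obtain stable variance estimates".

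The safety objective is descriptive: "To evaluate the frequency and severity of adverse events following vaccination" (Secondary Objectives). The safety analysis (Statistical Methods, Secondary Analyses, item 3) has two lines:

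- "Incidences of solicited local and systemic adverse events were summarized by frequency and percentage"
- "Group comparisons used Chi-square or Fisher's exact tests, as appropriate"

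For safety the protocol gives no contrast, risk difference or ratio, confidence interval, significance level or multiplicity rule. The primary analysis, by contrast, names its pair (co-administration and COVID-19-only) and reports a geometric mean ratio with a two-sided 95% CI.

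The Sample Size section adds a general caveat: "The study was not powered for confirmatory hypothesis testing; non-inferiority analyses are exploratory".

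**The concern.** The Background links the trial to co-administration policy. The safety question behind that is how many more participants have an AE with both vaccines than with one. The planned tests do not estimate this.

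- **If the test spans three arms**, it asks whether any arm differs. Should the two single vaccines differ in reactogenicity, it can be significant when co-administration adds nothing to the COVID-19 vaccine.
- **If the tests are pairwise**, 12 per arm leaves them unable to detect anything but a very large excess. For common events they may be unable to detect any excess.

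Because the contrast is open, the choice between these readings could be made after the data are seen. The trial's stated product is estimates for a definitive study, and a p-value does not supply one for safety.

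**Working it through.** **Inputs.** Three arms, 1:1:1, total 36 (Study Procedures; Sample Size). The plan's own figure reproduces: 3 × 12 = 36. It comes from a rule of thumb, so there is no power calculation to check. *Assumed, because the protocol gives neither:* AE rates, and a two-sided 0.05 level for safety tests. No dropout is allowed for.

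**1. Three-arm reading, one example.** Take 9/12, 3/12 and 9/12 with an AE (COVID-19-only, influenza-only, co-administration). In all, 21 of 36 have an event, so each arm expects 7 with and 5 without.

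χ² = (2² + 4² + 2²)/7 + (2² + 4² + 2²)/5 = 24/7 + 24/5 = 8.23 on 2 df, p = exp(−8.23/2) = 0.016.

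The exact Fisher-Freeman-Halton p is 0.028. Fisher's test of co-administration against COVID-19-only gives p = 1.00. The influenza-only arm produces the whole signal.

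**2. Three-arm reading, how often.** All 13³ outcome tables were enumerated, weighted by binomial probabilities, and those with p<0.05 summed. Co-administration and COVID-19-only have the same true rate in every row.

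| COVID-19-only / influenza-only / co-administration | Fisher-Freeman-Halton | Chi-square |
|---|---|---|
| 60/50/60% | 5% | 9% |
| 60/40/60% | 12% | 18% |
| 75/50/75% | 20% | 26% |
| 70/40/70% | 27% | 34% |
| 70/30/70% | 47% | 56% |
| 75/25/75% | 71% | 78% |

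At 75/25/75%, the pairwise Fisher test of co-administration against COVID-19-only is significant in 1.5% of trials.

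**3. Pairwise reading, power.** The same enumeration over 13² tables gives Fisher power of 9% for 50% against 70%, and 21% for 50% against 80%.

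**4. Pairwise reading, ceiling.** Suppose co-administration has 12/12 and COVID-19-only has x/12. The 12 − x non-events all fall in one arm, and the two-sided Fisher p is 2 × C(12, 12−x)/C(24, 12−x).

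- x = 6: 2 × 924/134,596 = 0.014. At x = 6 only 12/12 reaches significance; 11/12 gives p = 0.07.
- x = 8: 2 × 495/10,626 = 0.093.
- x = 9: 2 × 220/2,024 = 0.217.

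From 8/12 upward in COVID-19-only, no count in co-administration can give a significant excess.

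**5. What an interval would show.** Newcombe limits for p₁ − p₂ combine the Wilson limits (l, u) of each arm: lower = d − √[(p₁−l₁)² + (u₂−p₂)²], upper = d + √[(u₁−p₁)² + (p₂−l₂)²].

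For 10/12 against 6/12, the Wilson limits are 0.552–0.953 and 0.254–0.746, and d = 0.333.

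- Lower: 0.333 − √(0.281² + 0.246²) = −0.041.
- Upper: 0.333 + √(0.120² + 0.246²) = +0.607.

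The Fisher p is 0.19, while the estimate is +33 points (−4 to +61). Equal counts of 6/12 give 0 points (−35 to +35), and 9/12 in both give 0 points (−32.5 to +32.5), with p = 1.00 each time.

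**The case against.** Three stronger readings are tempting, and the protocol supports none of them.

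- **That safety is compared by a three-arm test.** A reader might infer this from the word for groups and the three-arm design. The text does not say it, and pairwise 2×2 tests fit equally well. Under pairwise testing, the comparison with COVID-19-only never involves the influenza arm. The firm defect is that the contrast is not named.
- **That safety rests on p-values alone.** Counts and percentages by group are also planned. A reader shown 9/12, 3/12 and 9/12 sees which arm differs and could derive an interval. A three-arm rejection at 75/25/75% is not a false positive either, since the arms do differ. It answers a different question.
- **That a non-significant result will be reported as safety.** Nowhere does the protocol say so. The objective is descriptive and the trial is declared not powered for confirmatory testing. This is a caution about interpretation, not an error in the text.

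The size also depends on assumptions. The 71–78% needs a 50-point gap between the single vaccines; at gaps of 10 to 30 points the range is 5–34%. The +61-point limit belongs to one chosen result with an observed 33-point excess. Low power comes from having 12 per arm, and a different analysis does not cure it.

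All of this stands. What remains is that the plan should state its own contrast and estimate rather than leave them to the reader, and should do so all the more because the tests are unpowered.

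**Conclusion.** The point holds in limited form. The protocol leaves the safety contrast open and specifies no between-group effect estimate or interval beyond counts and percentages. At 12 per arm, tests on either reading say little about what co-administration adds.

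A three-arm test can be moved by the influenza-only arm. How often depends on the assumed gap, from close to the nominal 5% at 10 points to 71–78% at 50 points. A pairwise Fisher test misses a 30-point rise (50% to 80%) in 79% of trials and cannot flag any excess when COVID-19-only is at 8/12 or higher. The AE rates and the 0.05 level are assumptions. The ceiling at 8/12 needs only the level and 12 per arm.

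Severity is minor: this is a secondary, descriptive outcome in a pilot, and the primary comparison is unaffected. It is worth changing because the improvement is cheap and serves the pilot's stated purpose of providing estimates.

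**What to change.** Replace the test sentence in the safety analysis with wording such as:

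*For each solicited AE, and for any local and any systemic AE, the risk difference with a score-based (Newcombe) 95% CI will be reported for co-administration versus COVID-19-only (main contrast) and versus influenza-only. Intervals are exploratory and unadjusted for multiplicity. Any p-values are descriptive, and the arms compared will be named. A non-significant difference will not be interpreted as evidence of equal safety.*

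Another score-based interval would serve as well, if named in advance.

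**Cost.** A few sentences and a few lines of R, with no new data. There are two downsides:

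- The intervals will be many and wide. Adverse Event Monitoring names nine solicited events (four local, five systemic). With the two composites and two contrasts that is (9 + 2) × 2 = 22 intervals, before any split by visit.
- Parts of the protocol are written in the past tense. If data are already in hand, the change must be disclosed as post hoc.
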